7. INVESTIGATIONAL PLAN

7.1. Overall Study Design

This is a Phase 2, randomized, double-blind, parallel-group, multicenter study of BA 180 mg and EZE 10 mg FDC versus PBO and EZE 10 mg administered for 12 weeks in subjects with T2D and elevated LDL-C. An overview of the study design is presented in Figure 1.

Figure 1: Overview of Study Design

T2D= type 2 diabetes; HbA1c = hemoglobin A1c; LDL-C = low-density lipoprotein cholesterol; LMT = lipid-modifying therapy; BA = bempedoic acid; EZE = ezetimibe; FDC = fixed dose combination.

Subjects with a history of T2D for at least 6 months will be screened for eligibility at an initial screening visit (Visit S1), which will be conducted approximately 42 days before planned randomization into the study. Subjects who have an LDL-C level >70 mg/dL and who meet all other inclusion/exclusion criteria will be return for Visit S2 approximately 5 weeks prior to planned randomization into the study to washout of all LDL-C-lowering therapies and begin taking single-blind (subject) PBO. Subjects will return to the study site approximately 7 days before planned randomization into the study for Visit S3. Subjects who have an LDL-C level ≥ 100 mg/dL and who continue to meet the study inclusion/exclusion criteria will be scheduled for their first treatment visit.

Subjects will report to the study site for the first treatment visit (Visit T1/Day 1) after a minimum 10-hour fast. Subjects who continue to meet the study inclusion/exclusion criteria will be randomized in a 1:1:1 ratio to receive either FDC (n = 56), EZE (n = 56), or PBO (n = 56) once daily for 12 weeks. Randomized subjects will return for clinic visits at Week 4 (Visit T2) and Week 12 (Visit T3/EOS). Subjects who withdraw from IMP treatment will be asked to continue to be followed for safety and efficacy using the protocol-specified visit schedule and procedures. Subjects will be dispensed IMP at Visit T1/Day 1 and will be instructed to take the IMP in the morning at 24-hour intervals, with approximately 8 ounces of water with or without food.

Subjects will report to each of the study visits after a minimum 10-hour fast and without having taken their dose of IMP. Study site personnel will administer the IMP on these days after blood

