11.7.1. Treatment Period Visit 1 (Visit T1/Day 1)

Subjects will be scheduled for their first treatment visit approximately 7 days after completion of Visit S3/Day -7. Subjects will arrive at the study site after a minimum 10-hour fast, will be administered their first dose of IMP at this visit.

Procedures and evaluations will be performed in the following order during this visit:

- Enrollment criteria will be reviewed.
- Concomitant and prohibited medications will be reviewed and recorded as needed.
- Adverse events will be assessed.
- Weight (in kilograms) will be recorded.
- Vital signs (systolic blood pressure, diastolic blood pressure, and pulse rate) will be recorded.
- Blood and urine specimens will be obtained for the following:
 - urine pregnancy test (for women of childbearing potential);
 - basic fasting lipid panel;
 - special lipids and other biomarkers;
 - clinical safety laboratories (hematology, clinical chemistry, and urinalysis);
 - reserve sample for potential exploratory biomarkers; and
 - urine drug screen.
- Subject will be given 1 serving of Ensure Original Vanilla[®] breakfast drink (Abbott Laboratories: 220 calories, 32 g of total carbohydrate) at approximately 9:00 AM and will record the time of the meal.
- Blood sample for PPG (glucose only) will be collected 2 hours \pm 5 minutes after the subject consumes the Ensure breakfast drink for the 2-hour postprandial glucose assessment.

- Subjects will be randomized to a treatment (once daily dosing of FDC, EZE, or PBO IMP).
- Double-blind IMP will be dispensed and subject will be provided with dosing and storage instructions.
- Subjects will take their first dose of IMP, with approximately 8 ounces of water, following collection of the 2-hour PPG blood glucose sample collection.
- Conduct diet and exercise counseling.

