13.6. Clinical Laboratory Tests

13.6.1. Clinical Safety Laboratory Parameters

Blood and urine specimens for safety laboratory assessments will be collected as shown in [Table 3](#).

Table 3: Clinical Safety Laboratory Evaluations

Clinical Laboratory Test	Clinical Laboratory Test
Hematology 
 • Hematocrit (Hct) • Hemoglobin (Hgb) • Mean corpuscular hemoglobin (MCH) • Mean corpuscular hemoglobin concentration (MCHC) • Mean corpuscular volume (MCV) • Platelet count • Red blood (RBC) cell count • White blood (WBC) cell count with differential (absolute and %) 	Blood Chemistry (serum, fasting) 
 • Albumin (Alb) • Alkaline phosphatase (ALK-P) • Alanine aminotransferase (ALT; serum glutamic pyruvic transaminase [SGPT]) • Aspartate aminotransferase (AST; serum glutamic oxaloacetic transaminase [SGOT]) • Blood urea nitrogen (BUN) • Calcium (Ca) • Carbon dioxide (CO₂) • Chloride (Cl) • Creatinine • Creatine kinase (CK) • Glucose • Lactate dehydrogenase (LDH) • Phosphorus • Potassium (K) • Sodium (Na) • Total bilirubin (TB)^a • Total protein • Uric acid
Urinalysis (Dipstick) 
 • Clarity • Bilirubin • Color • Glucose • Ketones • Leukocyte esterase • Nitrite • Occult blood • pH • Protein • Specific gravity • Urobilinogen 	Coagulation (Visit S1 for all subjects, Visit T1 and 3-7 days after Visit T1 in subjects receiving anticoagulation therapy only) 
 • Prothrombin time (PT) • International normalized ratio (INR)
Urinalysis (Microscopic)-only if urine dipstick abnormal 
 • Bacteria • Casts • Crystals • Epithelial cells • RBC • WBC 	

Table 3: Clinical Safety Laboratory Evaluations

Clinical Laboratory Test	Clinical Laboratory Test
Other Screening Labs	Additional samples

 • Hepatitis B surface antigen (HBsAg) • Hepatitis C virus (HCV)^b • Serum pregnancy test (only for females of childbearing potential) • Follicle-stimulating hormone (FSH; Females <55 years and ≥1 year without menses) • Urine pregnancy test prior to randomization (for female of child bearing potential) • Thyroid-stimulating hormone (TSH) 	
 • Hemoglobin A_{1C} (HbA_{1C})

^a If TB ≥1.2 × ULN, a reflex indirect (unconjugated) bilirubin will be obtained.

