^b If hepatitis C antibody (HCV-AB) is positive, a reflex HCV RNA will be performed to rule out active disease.

Subjects will be instructed to fast for a minimum of 10 hours before each blood draw; only water will be permitted during the fasting period. If the subject has not fasted for a minimum of 10 hours before the study visit, the blood sample will not be drawn at that visit. The reason for any missing blood samples will be documented.

When vital signs and blood samples for safety laboratories are to be collected at the same time, measurement of vital signs should precede collection of blood samples.

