13.6.3.1. Monitoring and Management of Elevated Liver Function Tests

If a subject has a new value $>3 \times \text{ULN}$ for serum ALT and/or AST at any time after randomization, the subject will undergo a repeat confirmatory liver function test (LFT) assessment as soon as is reasonably possible but preferably within 3 to 7 days after the laboratory result is available.

Repeat LFT assessment will include the following: (1) measurement of serum ALT, AST, alkaline phosphatase, TB, direct bilirubin, and CK; prothrombin time (PT)/international normalized ratio (INR); eosinophil count; and antihepatitis A virus (total), HBsAg (confirmation of screening measurement), HCV (confirmation of screening measurement), and anticytomegalovirus/immunoglobulin M; (2) history of concomitant medication use; (3) history of exposure to environmental chemical agents, including ethanol; and (4) questioning for related symptoms. Additionally, further testing, such as liver ultrasound or magnetic resonance imaging (MRI) scanning, may be warranted to rule out additional pathology depending on clinical presentation and should be discussed with the sponsor personnel or the authorized medical monitor.

- If the repeat LFT assessment confirms that the value for serum ALT and/or AST is $>3 \times \text{ULN}$, consideration should be given to withdrawing the subject and administering no further doses of IMP. At the investigator's discretion, IMP may be interrupted and the subject may be rechallenged with the IMP after values for the LFTs have returned to baseline levels.
- If repeat LFT assessment confirms a value for serum ALT and/or AST $>5 \times \text{ULN}$, the subject will be withdrawn from IMP treatment but will be asked to continue to be followed for safety (as outlined in the protocol-specified visit schedule in [Appendix 1](#) or more frequently as determined by the investigator).
- If repeat LFT assessment confirms that the value for serum ALT and/or AST level is $>3 \times \text{ULN}$ and the subject has any of the following findings, the subject will be withdrawn from IMP treatment but will be asked to continue to be followed for safety (as outlined in the protocol-specified visit schedule in [Appendix 1](#) or more frequently as determined by the investigator):
 - TB value $>2 \times \text{ULN}$;
Note: In the case of subjects with Gilbert's disease, TB will be fractionated and the determination of $2 \times \text{ULN}$ will be based upon direct (conjugated) bilirubin.

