13.6.3.3. Monitoring and Management of Changes in Hemoglobin Levels

If a subject experiences a decrease of >2.0 g/dL (20 g/L) from baseline in Hgb at any time after randomization, the subject will undergo a repeat confirmatory hematology testing as soon as is reasonably possible but preferably within 3 to 7 days after the laboratory test result becomes available.

Repeat hematology assessment will include the following: (1) measurement of Hgb, hematocrit (Hct), mean corpuscular hemoglobin (MCH), mean corpuscular hemoglobin concentration (MCHC), mean corpuscular volume (MCV), platelet count, reticulocyte count (percent and absolute), RBC count, and white blood cell (WBC) count with differential (absolute values only); (2) history of concomitant medication use; and (3) questioning for related symptoms. Additionally, further testing may be warranted to rule out additional pathology, depending on clinical presentation, and should be discussed with sponsor personnel or the authorized medical monitor.

- If a repeat assessment confirms a decrease >2.0 g/dL (20 g/L) from baseline in Hgb concentration, the subject should be monitored carefully during the study and return at 2-week intervals after study completion for additional Hgb measurements until the Hgb concentration returns to baseline or reaches a stable level.
- If a repeat assessment confirms a value <8 g/dL (80 g/L) for Hgb, the subject will be withdrawn from IMP treatment. The subject will return at 1-week intervals after withdrawal of IMP treatment for additional Hgb measurements until Hgb concentration returns to baseline or reaches a satisfactory conclusion.
- Subjects who are withdrawn from IMP treatment due to decreases in Hgb concentration will be asked to continue to be followed for safety (as outlined in the protocol-specified visit schedule in [Appendix 1](#)).

The investigator may choose to consult with a specialist at any time to further evaluate the cause of the alteration in hemoglobin.

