APPENDIX 1. SCHEDULE OF ASSESSMENTS

Study Period:	Screening and Run-in			Treatment			
Study Visit:	S1	S2	S3	T1	T2	T3/EOS ^a	
Study Week:	-6	-5	-1	1	4	12	
Procedure	Study Day:	-42 ± 7	-35 ± 3	-7 ± 3	1	28 ± 3	85 ± 3
Informed consent	X						
Inclusion/Exclusion criteria ^b	X	X	X	X			
Demographics	X						
Medical history	X						
Prior and/or Concomitant medications	X	X	X	X	X	X	
Adverse event recording		X	X	X	X	X	
Physical examination	X					X	
Weight/BMI ^c	X		X	X		X	
Height	X						
12-Lead ECG ^d		X					
Vital signs ^e	X	X	X	X	X	X	
Serum pregnancy test/FSH ^f	X						
Urine pregnancy test ^h				X		X	
Basic fasting lipid panel ^g	X		X	X	X	X	
Special lipids and other biomarkers ^h	X			X	X	X	
Coagulation panel ⁱ	X						
TSH	X						
Serology ^j		X					
Clinical safety laboratories ^k	X		X	X	X	X	
Urine drug screen	X			X			

Study Period:	Screening and Run-in			Treatment			
Study Visit:	S1	S2	S3	T1	T2	T3/EOS ^a	
Study Week:	-6	-5	-1	1	4	12	
Procedure	Study Day:	-42 ± 7	-35 ± 3	-7 ± 3	1	28 ± 3	85 ± 3
Reserve Sample for Potential Exploratory Biomarkers ¹				X		X	
Calculate eGFR	X						
Washout LMT		X	X	X	X	X	
Randomization				X			
Ensure breakfast drink ^m				X	X	X	
PPG glucose sample ⁿ				X	X	X	
Diet and exercise counseling	X	X	X	X	X		
Dispense single-blind IMP		X					
Return single-blind IMP and assess dosing adherence			X	X			
Dispense double-blind IMP				X	X		
Return double-blind IMP and assess dosing adherence					X	X	

ApoB = apoprotein B; BMI = body mass index; ECG = electrocardiogram; eGFR = estimated glomerular filtration rate; EOS = end of study; FSH = follicle-stimulating hormone; HbA1c = hemoglobin A1c; HbsAg = hepatitis B surface antigen; HCV-AB = hepatitis C virus antibody; HDL-C = high-density lipoprotein cholesterol; hs-CRP = high-sensitivity C-reactive protein; IMP = investigational medicinal product; LDL-C = low-density lipoprotein cholesterol; TC = total cholesterol; TG = triglycerides; TSH = thyroid-stimulating hormone.

^a All procedures will be completed at EOS or at time of early termination from the study. The last dose of IMP will be taken on the morning of Day 84 or the day prior to Visit T3/EOS. Visit T3/Day 85 represents 24 hours after the last dose of IMP.

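### Under the rule that an unfasted subject has no blood drawn, with no recollection required, a subject unfasted at Week 4 can finish dosing with no scheduled post-baseline hematology or chemistry result

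*Protocol*

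**What the plan says.** Protocol Section 13.6.1, below Table 3, states that if a subject "has not fasted for a minimum of 10 hours before the study visit, the blood sample will not be drawn at that visit". The only consequence it gives is this: "The reason for any missing blood samples will be documented". No test is exempted and no return for the missed sample is required.

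In Table 3 only the chemistry block is headed as fasting ("Blood Chemistry (serum, fasting"). Hematology, including hemoglobin, and HbA1c stand in the same table without that label.

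Appendix 1 schedules safety laboratories at S1, S3, T1, T2 and T3. The T1 blood is taken before treatment starts: "Subjects will take their first dose of IMP, with approximately 8 ounces of water, following collection of the 2-hour PPG blood glucose sample collection". The T3 blood is taken after treatment ends: "The last dose of IMP will be taken on the morning of Day 84 or the day prior to Visit T3/EOS".

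The laboratory-driven rules in Section 13.6.3 need a drawn value. For ALT/AST, a new elevation "at any time after randomization, the subject will undergo a repeat confirmatory liver function test (LFT) assessment". For hemoglobin: "If a repeat assessment confirms a value <8 g/dL (80 g/L) for Hgb, the subject will be withdrawn from IMP treatment". Sections 13.6.3.2 and 13.6.3.4 do the same for eGFR and CK.

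**The concern.** The rule protects the lipid and glucose data, where fasting matters to the endpoints. It is written for the whole blood draw, however, and it sits in the safety laboratory section. A subject who eats breakfast before T2 therefore gives no hemoglobin sample, although nothing in Table 3 ties hemoglobin to fasting. That subject also gives no liver, muscle or renal chemistry, and the protocol does not require anyone to bring the subject back.

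The interruption and withdrawal rules in Section 13.6.3 can act on scheduled data only if a sample is drawn while dosing is still to follow. The T2 procedures in Section 11.7.2 do not make the second dispensing of double-blind drug depend on blood having been taken. For such a subject, about eight more weeks of drug can be supplied with no hematology or chemistry result since baseline.

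Efficacy is touched as well. An unfasted T3 visit loses the Week 12 LDL-C, which then falls to LOCF (Protocol 14.6, SAP 5.3.2), and it loses the end-of-treatment safety bloods, which SAP 5.5.3 does not impute.

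**Working it through.** No sample-size, power or alpha figure bears on this point, and the plan gives no figure of its own to reproduce. The check is a count of scheduled draws and the intervals between them.

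**1. Scheduled hematology and chemistry draws from T1 onward** (Appendix 1; Sections 11.7.1 to 11.7.3)

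| Visit | Day | Position relative to dosing | Dosing still to follow after a post-baseline result? |
|---|---|---|---|
| T1 | 1 | before the first dose | no, this is baseline |
| T2 | 28 ± 3 | on drug, before that day's dose | yes |
| T3/EOS | 85 ± 3 | about 24 hours after the last dose | no, dosing has ended |

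Post-baseline draws with dosing still to follow: 1 (T2). If the T2 blood is not drawn: 1 − 1 = 0.

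**2. Gaps between scheduled safety bloods**

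- As scheduled, T1 to T2: 28 − 1 = 27 days (24 to 30 with the T2 window).
- As scheduled, T2 to T3: 85 − 28 = 57 days (82 − 31 = 51 to 88 − 25 = 63 with both windows).
- T2 not drawn, T1 to T3: 85 − 1 = 84 days (81 to 87 with the T3 window).

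The longest nominal gap rises from 57 to 84 days, which spans the whole dosing period.

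**3. Whether another provision requires a redraw**

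- Section 11.4 lets a subject be seen at any time for safety. This is permission, not tied to a missed sample.
- Section 11.8.2 asks that every effort be made to complete visits on schedule and lets the sponsor consider early or late visits to prevent withdrawal. It does not address an attended visit with no blood drawn.
- Section 13.6.3 lets the investigator repeat or add tests to verify an original result, which presupposes that one exists.
- SAP 5.1 slots Day 2 to 56 as Week 4 and Day 57 onward as Week 12, and SAP 5.5.3 counts unscheduled laboratory assessments when identifying abnormalities. A redraw could be analysed.

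A redraw is therefore allowed and usable, but nothing obliges the site to do one.

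**4. Effect on LDL-C**

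If T3 is not drawn, LOCF uses the last post-baseline value, which can come only from T2, 57 nominal days earlier. If T2 was also undrawn, there is no post-baseline value to carry forward.

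**5. Number of subjects**

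The documents give no rate of unfasted arrival. The range below is an assumption: rate × N, with N = 168 (protocol) or 234 (SAP), and with nobody brought back.

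- 2% × 168 = 3.4; 5% × 168 = 8.4
- 2% × 234 = 4.7; 5% × 234 = 11.7

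That is about 3 to 12 subjects per visit. For a given rate it is an upper bound, since any recollection lowers it.

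**6. What counts as fasted**

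Section 8.3 permits water and concomitant medications during the fast. Section 13.6.1 permits only water, and Section 11.7 uses a water-only instruction before T1. Inclusion criterion 3 requires every subject to be on stable diabetes medication. On a literal reading of 13.6.1, a site could class a subject who took a morning tablet as unfasted and cancel all blood. These passages must be reconciled.

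**The case against.** The best defence is that a uniform fasting draw is a coherent choice for a trial with lipid and glucose endpoints. Sections 8.3, 11.5 and 12.1.1 tell subjects and sites that laboratory samples are taken fasted. The rule applies only to that visit, the ±3-day windows leave room for a return, and the laboratory manual, which is not among the documents, may contain a redraw procedure. All of this stands, and it limits the point to a rule that does not require recollection. It does not show that the samples cannot be recovered.

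Three stronger readings are tempting but not supported:

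- A reader might infer that ALT, AST, CK and creatinine are non-fasting tests cancelled needlessly. Table 3 and the synopsis label the whole chemistry panel as fasting, and no section says these analytes may be read unfasted. On the protocol's own labels, the unnecessary loss is hematology and HbA1c.
- A reader might infer that T2 is the only laboratory check on drug. The rule covers blood only, so the T2 urinalysis remains. Subjects on an anticoagulant also have PT/INR 3 to 7 days after starting drug. The T3 sample, about 24 hours after the last dose, still reflects exposure; it simply comes too late to act on dosing.
- A reader might infer that 3 to 12 subjects will lose their results. That count needs both an assumed rate and the assumption that no one returns.

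**Conclusion.** The point holds in a limited form. Followed exactly, Section 13.6.1 cancels two tests that Table 3 does not label as fasting, and it requires no recollection of any test. At T2 this removes the one scheduled hematology and chemistry draw on which the Section 13.6.3 rules could act during dosing. Scheduled looks of that kind fall from 1 to 0 for the subject concerned.

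The count of draws and the 57- and 84-day gaps follow from the schedule at nominal visit days. The number of subjects does not: it rests on an assumed 2-5% rate and no returns. The effect is likely to be confined to a few subjects, but for them it bears on safety monitoring, and the rule is cheap to change. It should be changed.

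**What to change.** In Section 13.6.1:

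- Limit the no-draw rule to samples the protocol labels as fasting: lipids, fasting glucose with the PPG test, and chemistry as labelled in Table 3. Draw hematology and HbA1c at the visit whatever the fasting status. Sections 11.5 and 12.1.1, which list these samples among those taken fasted, need a matching exception.
- Require missed fasting samples, including the chemistry panel, to be recollected within the existing ±3-day window or as soon as possible after it.
- Record fasting status on the eCRF.
- Have the sponsor state whether any chemistry analytes may be drawn unfasted.
- Reconcile the fasting definitions in Sections 8.3, 11.7 and 13.6.1.

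In the SAP, add to Section 5.1 that the fasting value is used when two results of the same test fall in one visit window; no selection rule is given there now. The windows themselves need no change.

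A T3 recollection needs a further sentence. Dosing has ended by then, Section 11.7.3 allows lipid-modifying therapy to restart when the visit concludes, and the protocol's FAS definition (though not the SAP's) ties lipid values to drug taken within 2 days. The sponsor should say how a late T3 lipid sample fits with these passages.

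Cost: a paragraph in 13.6.1 with matching edits to the sections named above and the laboratory manual, one eCRF field, two SAP sentences, and a return draw for a few subjects.

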13.6.2. Sample Collection, Storage, and Shipping

Blood samples will be drawn with the subject in the seated position. Laboratory samples will be collected by appropriate clinical site personnel and then shipped according to the instructions in the laboratory manual (provided by the central laboratory).

13.6.3. General Monitoring and Management of Abnormal Clinical Laboratory Values

The investigator will review the results of all laboratory tests as they become available and will sign and date the report to document their review. The investigator will ascertain if any laboratory value is abnormal or represents a clinically significant change from baseline for the individual subject, with baseline defined as the last value or observation before the first dose of IMP. The investigator may repeat the laboratory test or request additional tests to verify the results of the original laboratory test.

If a laboratory value is determined to be an abnormal and clinically significant change from baseline for the subject, the investigator will determine if it qualifies as an AE (as described below), and if yes, an appropriate eCRF will be completed. All clinically significant laboratory abnormalities that occur during the study that were not present at baseline should be followed and evaluated with additional tests, if necessary, until diagnosis of the underlying cause or resolution. Specific monitoring and management guidelines for laboratories of special interest are outlined in the sections below.

An abnormal laboratory value that is not already associated with an AE is to be recorded as an AE only if any one of the following criteria is met:

- an action is taken with the imp because of the abnormality;
- intervention for management of the abnormality is required; or
- the abnormality be deemed clinically significant by the investigator.

